### **3.4.2.4 Progression-free Survival**

Progression-free survival (PFS) is defined as the time from randomization until the first documentation of a disease progression or death due to any cause, whichever occurs first, regardless of whether the subject receives subsequent anticancer treatment prior to progression. Subjects who have no documented progression and are still alive at the time of analysis will be censored at the time of the latest date of assessment from their last evaluable RECIST v1.1 assessment. PFS is defined in months as follows:

$$\text{PFS (months)} = (\text{Date of PD/death or censoring} - \text{Date of randomization} + 1) / (365.25/12),$$

The censoring guidance and the date of PD/death or censoring are given in the table below. The number and percentage of subjects experiencing a PFS event and Kaplan-Meier plots of PFS will be presented by treatment group. The median PFS and its 95% CI will be estimated using the Kaplan-Meier method. The proportion of subjects progression-free and alive at 12

months (PFS-12) and associated 95% CI will be estimated using the Kaplan-Meier method. Additional PFS landmarks to be included in the final analysis are PFS-18, PFS-24, and PFS-36.

The difference in PFS between each experimental arm and control arm will be tested for significance by using a stratified log-rank test on histology (adenocarcinoma vs non-adenocarcinoma). The log-rank test will be carried out with the Breslow method for handling ties. The hazard ratio (HR) (experimental vs. control) with two-sided 95% CI will be estimated by stratified Cox regression model on histology with ties handled by the Efron method ([Efron et al, 1977](#)).

The comparison of PFS-X (X=12, 18, 24, 36 months) between each experimental arm and control arm will be performed by normal approximation under complementary loglog (cloglog) transformation ([Klein et al, 2007](#)). The test statistic shown below asymptotically follows a chi-square distribution with one degree of freedom under the null hypothesis  $H_0: S_1(t) = S_2(t)$ .

$$X^2 = \frac{\left( \log(-\log(\hat{S}_1(t))) - \log(-\log(\hat{S}_2(t))) \right)^2}{\hat{\sigma}_1(t)^2 / \left( \log(\hat{S}_1(t)) \right)^2 + \hat{\sigma}_2(t)^2 / \left( \log(\hat{S}_2(t)) \right)^2}$$

where

- $\hat{S}_k(t)$ , with  $k = 1, 2$  is the Kaplan-Meier estimate of the survival function for the  $k$ th treatment group
- $\hat{\sigma}_k(t)^2 = \sum_{t_{ki} \leq t} \frac{d_{ki}}{n_{ki}(n_{ki} - d_{ki})}$  (Greenwood's formula) is from the estimated variance  $\hat{V}(\hat{S}_k(t)) = \hat{S}_k(t)^2 \hat{\sigma}_k(t)^2$  of the KM estimate  $\hat{S}_k(t)$  with  $k = 1, 2$
- $d_{ki}$  refers to the number of events (i.e., deaths or disease progressions) at time  $t_{ki}$
- $n_{ki}$  refers to the number of subjects at risk at time  $t_{ki}$

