### **4.6 Treatment Assignment and Blinding**

#### **4.6.1 Methods for Assigning Treatment Groups**

Once confirmed that the subject meets eligibility criteria, an IXRS will randomize the subject to a treatment arm according to the randomization scheme.

A randomization method with dynamically changing randomization ratios will be employed to account for fluctuation in the number of treatment arms open for enrollment over the course of the study. Randomization will be stratified by histology (adenocarcinoma vs non-adenocarcinoma). The randomization scheme will use an equal ratio to all study treatment arms open for enrollment (eg, if experimental arms are opened sequentially, an experimental arm is added/closed, or enrollment in an experimental arm is suspended). Additionally, the following considerations regarding randomization will apply:

- If there is no experimental arm open for enrollment, then enrollment will be paused. Any subject who had consented previously and was in screening when the experimental arm(s) was closed due to safety concerns may be allowed to enter into the study but must be allocated to the control arm.
- Once the control arm enrolls 60 subjects, a subsequent randomization scheme may be initiated to optimize the number of subjects allocated to control arm.
- At any point during the study, the control arm will have no less than a 33% chance to be randomized in comparison to the active experimental arm that has the lowest randomization ratio in the study.

Study treatment must be administered within 3 days after the treatment arm is assigned. If there is a delay in the administration of study treatment such that it will not be administered within the specified timeframe, the study monitor must be notified immediately.

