#### **4.8.3.2 Secondary Efficacy Analyses**

Secondary efficacy endpoints include DoR, DC, PFS, and OS. Analyses of secondary endpoints will be performed as follows.

- DoR according to RECIST v1.1 will be analyzed using the Kaplan-Meier method for those subjects with OR in the corresponding analysis populations. The median of DoR with 95% CI will be estimated based on the Kaplan-Meier curves.
- The DCR according to RECIST v1.1 is defined as the proportion of subjects with DC. The 2-sided 95% CI of DCR will be provided using an exact probability method. DCR at 16 weeks will be estimated along with the 2-sided 95% CI.
- PFS according to RECIST v1.1 will be analyzed using the Kaplan-Meier method. The median PFS with 95% CI will be estimated based on the Kaplan-Meier curves. PFS-12 will be estimated based on the Kaplan-Meier curves along with their 95% CIs when applicable. An estimate of the difference in PFS-12 between an experimental arm and the control arm will be reported. Comparison of treatment arms for PFS-12 will be performed under complementary log-log transformation of the Kaplan-Meier estimates of PFS-12 (Klein et al, 2007)
- OS will be analyzed using the Kaplan-Meier method. The median OS with 95% CI will be estimated based on the Kaplan-Meier curves. The 1-year OS rates will be estimated based on the Kaplan-Meier curves along with their 2-sided 95% CI when applicable.

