## 2.3 Treatment Assignment and Blinding

### Treatment Assignment

An interactive voice/web response system (IxRS) will be used to assign investigational product (IP) kit numbers to each subject who meets the eligibility criteria. A randomization method with dynamically changing randomization ratios will be employed to account for fluctuation in the number of treatment arms open for enrollment over the course of the study. The randomization will be stratified by histology (adenocarcinoma vs non-adenocarcinoma) and will use an equal ratio to all study treatment arms open for enrollment (e.g., if experimental arms are opened sequentially, an experimental arm is added/closed, or enrollment in an experimental arm is suspended). Additionally, the following considerations regarding randomization will apply:

- If there is no experimental arm open for enrollment, then enrollment will be paused. Any subject who had consented previously and was in screening when the experimental arm(s) was closed due to safety concerns may be allowed to enter into the study but must be allocated to the control arm.

- Once the control arm enrolls 60 subjects, a subsequent randomization scheme may be initiated to optimize the number of subjects allocated to control arm.
- At any point during the study, the control arm will have no less than a 33% chance to be randomized in comparison to the active experimental arm that has the lowest randomization ratio in the study.

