### **2.4 Sample Size**

Sixty subjects will be enrolled in each of the combination therapy experimental arms and more than 60 subjects will be enrolled in the durvalumab control arm dependent upon the length of the study. The sample size of 60 subjects per experimental arm is not designed to make explicit power and Type I error considerations for a hypothesis test. It is primarily chosen to obtain a preliminary assessment of antitumor activity with a certain degree of precision.

Table 2.4-1 shows estimated differences in objective response rate (ORR) between an experimental arm and control arm along with 2-sided 95% exact CIs with a sample size of 60 subjects each. Sixty subjects per treatment arm provides a 95% CI with reasonable width (approximately  $\pm 18\%$ ) for the estimated ORR difference between a durvalumab combination experimental arm and the durvalumab control arm. For a 20% increase in ORR in any durvalumab combination experimental arm over durvalumab control arm (50% vs 30%, respectively), the lower limit of the 95% CI for the difference between these arms is 1%, which is greater than 0%, suggesting that the durvalumab combination experimental arm will have a higher ORR than the durvalumab control arm with 95% confidence.

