### 3.4.2.5 Overall Survival

Overall survival (OS) is defined as the time from randomization until death due to any cause. A subject alive at the end of study or lost to follow-up will be censored for OS at the last date when the subject was known to be alive. The last date for each individual subject is defined as the latest among the following dates recorded on the case report forms (CRFs):

- AE start, stop, and change dates
- Admission and discharge dates of hospitalization
- Start date of protocol deviations
- Study treatment date
- Date of last contact, withdrawal consent, refuse to be followed up, or last known alive on end of treatment, end of study, and survival status/follow-up CRFs
- Laboratory test dates including (but not limited to) hematology, chemistry, urinalysis, coagulation, tumor biopsy, immunoglobin, pharmacokinetics, pharmacodynamic biomarkers.
- Disease assessment dates on RECIST CRF
- Date of visit, vital signs, ECOG, electrocardiogram, and physical examination
- Start and stop dates of alternative anticancer treatment
- Start and end date of concomitant medication and surgical/medical procedure

OS is defined in months as follows:

$$\text{OS (months)} = (\text{Date of death or censoring} - \text{Date of randomization} + 1) / (365.25/12).$$

The number and percentage of subjects experiencing an OS event and Kaplan-Meier plots of OS will be presented by treatment group. The median OS and its 95% CI will be estimated using the Kaplan-Meier method. The proportion of subjects alive at 12 months (OS-12) and

associated 95% CI will be estimated using the Kaplan-Meier method. Additional OS landmarks to be included in the final analysis are OS-18, OS-24, and OS-36.

The difference in OS between groups will be tested for significance by using a stratified log-rank test on histology (adenocarcinoma vs non-adenocarcinoma). The log-rank test will be carried out with the Breslow method for handling ties. The hazard ratios of each experimental arm vs. control arm with two-sided 95% CI will be estimated by a stratified Cox regression model on histology with ties handled by the Efron method ([Efron et al, 1977](#)).

The comparison of OS-X (X=12, 18, 24, 36 months) between the 2 treatment arms will be performed by normal approximation under cloglog transformation ([Klein et al, 2007](#)), where the event is death. The test statistic is defined in Section [3.4.2.4](#).

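### The PFS and OS landmark comparisons leave out the histology stratum used in randomisation; if histology is prognostic they are mildly conservative

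*SAP*

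**What the plan says.** Protocol 4.6.1 sets the design: "Randomization will be stratified by histology (adenocarcinoma vs non-adenocarcinoma"). SAP 2.3 repeats this and says that the scheme "will use an equal ratio to all study treatment arms open for enrollment".

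The SAP uses the stratum in three places. The primary ORR comparison is a Cochran-Mantel-Haenszel test stratified by histology (3.4.1.1). PFS is "tested for significance by using a stratified log-rank test on histology", with a Cox model stratified in the same way (3.4.2.4). OS is treated like PFS (3.4.2.5).

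The landmark comparisons differ. In SAP 3.4.2.4 the PFS-12, -18, -24 and -36 comparison "between each experimental arm and control arm will be performed by normal approximation under complementary loglog (cloglog) transformation". The formula printed there takes one Kaplan-Meier estimate and one Greenwood sum per treatment group and refers the result to chi-square with 1 degree of freedom. In SAP 3.4.2.5 the OS-X comparison "between the 2 treatment arms will be performed by normal approximation under cloglog transformation", using the same statistic. Neither has a stratum term, and no reason is given.

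PFS-12 is a named secondary endpoint (Protocol Table 2; SAP 3.4.2). Protocol 4.8.3.2 also specifies the complementary log-log comparison without stratification, and adds: "An estimate of the difference in PFS-12 between an experimental arm and the control arm will be reported". Neither document gives a variance or CI for that difference.

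**The concern.** Stratified allocation balances histology across arms, so the between-histology part of the variance drops out of the arm difference. A Greenwood variance computed on the pooled arm still contains it. When histology predicts PFS, the denominator of the landmark statistic is therefore too large, the statistic is too small, and the chi-square reference distribution is not quite right.

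At stake is some precision on a secondary endpoint, in a trial whose sample size was justified by precision. There is also an unexplained inconsistency: two analyses of the same PFS data treat the randomisation stratum differently, so a reader cannot tell how much of any disagreement between the log-rank and PFS-12 results comes from that.

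**Working it through.** **The plan's own figures.** The documents state no power, alpha or sample size for any landmark test. The nearest design figure is the ORR precision table (SAP Table 2.4-1, Protocol Table 9). An exact unconditional 95% interval with 60 per arm reproduces its four rows against 18/60: (−8.7%, 28.2%), (−3.7%, 33.0%), (1.3%, 37.7%) and (6.4%, 42.3%).

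**Inputs from the documents.**
- n: "Sixty subjects will be enrolled in each of the combination therapy experimental arms" (SAP 2.4). With an equal ratio, 60 concurrent controls are taken per comparison.
- Control PFS level: median 17.2 months in the phase 3 trial cited in Protocol 1.1. Assuming exponential times, S(12) = exp(−ln 2 × 12/17.2) = 0.617.

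**Assumptions, not in the documents.** Two-sided 5% level; histology mix f = 50:50 (65:35 as a check); gap d in 12-month PFS between strata of 0 to 40 points; HR 0.45 (about 62% vs 80%); exponential times; about 10% censored by month 12.

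**Size, analytic (censoring ignored).** The between-stratum share of the pooled variance is h = f(1−f)d² / [S(1−S)]. The true variance of the arm difference is (1−h) times the value the test uses, so

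size = 2 × [1 − Φ(1.96/√(1−h))].

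For d = 20 points: h = 0.25 × 0.04 / (0.617 × 0.383) = 0.0423, 1.96/√0.9577 = 2.003, size 4.52%. The pooled standard error is too large by the factor 1/√(1−h): 0.5%, 2.2%, 5.1% and 9.7% for gaps of 10, 20, 30 and 40 points.

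**Simulation (40,000 runs per setting, 50:50 mix).** The SAP statistic was compared with the same chi-square on histology-standardised Kaplan-Meier estimates.

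| Gap d (points) | Analytic size, SAP test | Simulated size, SAP / standardised | Power at HR 0.45, SAP / standardised | Difference | Net of d = 0 |
|---|---|---|---|---|---|
| 0 | 5.00% | 4.9 / 5.1% | 59.22 / 59.95% | 0.73 | 0 |
| 10 | 4.88% | 4.8 / 5.1% | 58.36 / 59.40% | 1.04 | 0.3 |
| 20 | 4.52% | 4.5 / 5.1% | 57.76 / 59.66% | 1.90 | 1.2 |
| 30 | 3.94% | 3.7 / 4.9% | 55.89 / 59.62% | 3.73 | 3.0 |
| 40 | 3.15% | 3.0 / 5.0% | 54.05 / 60.06% | 6.01 | 5.3 |

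The 0.73-point difference at d = 0 cannot come from stratification. It is a finite-sample difference between the two statistics, so it is subtracted in the last column. Monte Carlo standard error is about 0.1 point for size and 0.25 point for power, so the 0.3-point loss at d = 10 is close to noise.

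**Sensitivity.**
- 65:35 mix: analytic size 4.89%, 4.56%, 4.03% and 3.31% for gaps of 10 to 40 points.
- HR 0.55, 50:50 mix, a separate simulation of 8,000 runs: SAP vs standardised power is 38.4 vs 39.2% (no gap), 38.5 vs 40.1% (strata 70/53%), 36.8 vs 40.0% (75/48%) and 34.3 vs 40.0% (80/43%). Net of the no-gap difference of 0.8, the losses are 0.8, 2.4 and 4.9 points.

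**The form of stratification matters.** Inverse-variance pooling of per-stratum cloglog differences gave power of 55.3%, 55.0%, 55.9%, 56.8% and 59.5% for gaps of 0 to 40 points. That is below the SAP test up to 20 points and above it only from 30.

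**The case against.** The case for leaving the plan alone is reasonable. Protocol 4.8.3.2 specifies the same unstratified comparison, so the SAP follows it. Both documents say that the sample size was not set by power or type I error. Go and No-Go decisions rest on ORR and DCR, not PFS-12. The stratified log-rank and Cox analyses already give stratum-adjusted inference on PFS. All of this stands, and it keeps the point modest. It does not explain why the landmarks differ from the other stratified analyses, and a precision rationale is no reason to use a variance that may be overstated.

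A reader might go further and infer that the landmark tests certainly lose power, or that they fail to control error. The documents support neither reading. Any loss depends on how prognostic histology is, which they do not report, and nothing in them points to a gap as large as 30 points. A conservative test keeps its false-positive rate at or below the nominal level. A reader might also blame the missing stratum for any conflict between the PFS-12 and log-rank p-values. They test different hypotheses (one time point against the whole curve) and can disagree anyway. Nor can a planned CI for the PFS-12 difference be called too wide, since none is specified.

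It is also fair to object that stratifying does not help automatically, as inverse-variance pooling shows, and that a discretionary return to the unstratified test at late landmarks would be a data-dependent choice. Both limit the form of the remedy.

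**Conclusion.** The inconsistency is real, and its direction is conservative if histology is prognostic. Under the assumptions above it is small for gaps up to 20 points (size about 4.5% or more, net power loss about 1 point or less). It becomes material only at 30 to 40 points (size about 3.9% to 3.2%, net loss 3 to 5 points). Without a prognostic effect there is no stratification-related loss. The SAP test remains a valid test of equal survival at the landmark.

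The change is still worth making. PFS-12 is a named secondary endpoint, the standardised test held a size of about 5% and had at least as much power in every setting simulated, and the cost is close to nil.

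**What to change.** In SAP 3.4.2.4 and 3.4.2.5, for PFS-12 and for the other landmarks where estimable:

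- Estimate each arm's landmark survival as S_k(t) = Σ_s w_s S_ks(t). The weight w_s is the overall proportion of subjects in histology stratum s across the two arms compared.
- Take V_k = Σ_s w_s² × (Greenwood variance of S_ks(t)). The SAP formula uses the Greenwood sum rather than the variance of S, so V_k/S_k(t)² replaces its σ² term. The cloglog chi-square is otherwise unchanged.
- Do not substitute inverse-variance pooling of per-stratum cloglog differences.
- Report the PFS-12 difference with a 95% CI from the same standardised estimates. This also supplies a method for the estimate promised in the protocol.
- Keep the unstratified test as a sensitivity analysis.
- Fix the fallback in advance, by a rule that does not depend on the treatment comparison. For example, use the unstratified test at a landmark when any stratum-by-arm cell has fewer than a stated number at risk, or has a Kaplan-Meier estimate of 0 or 1.

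The cost is SAP wording and a few lines of programming, with no new data. The downside is less stable estimates at late landmarks in the smaller stratum: a 50:50 mix leaves about 30 subjects per stratum and arm at the start, and an uneven mix leaves fewer in one of them.

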**Table 3.4.1      Summary of Censoring Guidelines for PFS**

Situation	Date of PD/Death or Censoring	PFS Outcome
Documented Progressive Disease (PD) or death	Date of earliest sign of PD or death, whichever comes first	Event (unless the censoring rule specified below)
Death or PD immediately after $\geq 2$ consecutive missed or non-evaluable disease assessments as per the protocol specified assessment schedule	Date of last progression-free disease assessment prior to missed or non-evaluable assessments, or randomization, whichever occurred last	Censored
No PD or death at time of analysis or lost to follow-up	Date of last evaluable progression-free disease assessment	Censored
No tumor assessment at baseline and no evidence of PD at first post-baseline disease assessment OR No tumor assessment post-first dose, and no death prior to second scheduled post-baseline disease assessment	Date of randomization	Censored

PD = progressive disease; PFS = progression-free survival.

Subjects having missing lesion data at baseline or no disease assessments post-first dose of IP will have PFS censored at the date of randomization unless the subject dies prior to the second scheduled post-baseline disease assessment in which case the death date will qualify as a PFS event.

If a subject has two or more consecutive completely missed or non-evaluable assessments followed immediately by death or an assessment showing radiologic disease progression, then the subject will be censored for PFS. PFS will be censored at the date of randomization or the last progression-free disease assessment prior to the missed or non-evaluable assessments, whichever occurred last.

If a subject has two or more consecutively missed or non-evaluable assessments followed by an assessment showing no radiologic disease progression, then the assumption will be that the subject did not progress during the missed or non-evaluable assessments.

The length of gap (in number of days) to determine two or more consecutive assessments is defined as the following:

- 126 days during the first 12 months (A 8-week disease assessment interval plus a 7-day window for each assessment).

- 182 days from month 12 to month 24 (A 12-week disease assessment interval plus a 7-day window for each assessment).
- 422 days after month 24 (A 6-month disease assessment interval plus a 4-week window for each assessment).

Subjects remaining on study without radiologic disease progression or death at the time of analysis will be censored for PFS at the date of their last evaluable disease assessment.

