- PFS, defined as the time from randomization until the first documentation of disease progression according to RECIST v1.1 or death due to any cause, whichever occurs first, regardless of whether the subject receives subsequent anticancer therapy prior to progression. Subjects who are alive progression free at the time of DCO will be censored on the date of their last evaluable tumor assessment. PFS-12 will be estimated using the Kaplan-Meier method.

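### SAP 3.4.2.4 gives two incompatible PFS censoring rules for subjects with missing baseline tumour data, and both depart from the protocol's PFS definition

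*SAP*

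**What the plan says.** Protocol 4.8.3 sets the endpoint: "PFS, defined as the time from randomization until the first documentation of disease progression according to RECIST v1.1 or death due to any cause". The only censoring rule it gives is "Subjects who are alive progression free at the time of DCO will be censored on the date of their last evaluable tumor assessment". It leaves further detail to the SAP, and SAP 3.4.2.4 opens with the same definition of an event.

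SAP Table 3.4.1 starts from a default in which documented progression or death is "Event (unless the censoring rule specified below" applies. Its last row censors at randomization in two situations. The first is "No tumor assessment at baseline and no evidence of PD at first post-baseline disease assessment". The second is "No tumor assessment post-first dose, and no death prior to second scheduled post-baseline disease assessment".

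The sentence below the table merges the two situations: "Subjects having missing lesion data at baseline or no disease assessments post-first dose of IP will have PFS censored at the date of randomization". It allows a single exception, which serves both groups and concerns early death only: "unless the subject dies prior to the second scheduled post-baseline disease assessment in which case the death date will qualify as a PFS event".

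**The concern.** The table and the sentence describe the same group of subjects but attach different conditions to them.

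- **Exception.** In the table, the baseline clause is lifted by progression at the first scan, and the clause for no post-dose assessment is lifted by early death. In the sentence, early death lifts both, and progression at the first scan lifts neither.
- **Trigger.** The table needs the baseline assessment to be absent. The sentence needs only baseline lesion data to be missing, and it does not say whether one absent measurement is enough.

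Two programmers who each followed the section faithfully could therefore code different events. Under either rule, some progressions and deaths that the protocol counts are replaced by zero follow-up. PFS and PFS-12 are named secondary endpoints. SAP 3.4.2.4 gives them a stratified log-rank test, a Cox hazard ratio and landmark comparisons out to 36 months. The study is open-label, so event wording is better settled before the results are known.

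**Working it through.** The documents give no figure to reproduce, so the check sets the rules side by side. For a subject with no baseline assessment:

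| Course | Sentence below table | Table 3.4.1, read literally | Protocol 4.8.3 |
|---|---|---|---|
| PD at first scan, alive at second scheduled scan | Censored at randomization | Event | Event |
| No PD at first scan, death before second scheduled scan | Event | Censored at randomization | Event |
| First PD at second scan or later | Censored at randomization | Censored at randomization | Event |
| No PD at first scan, death after second scheduled scan | Censored at randomization | Censored at randomization | Event |
| Alive and progression-free | Censored at randomization | Censored at randomization | Censored at last evaluable assessment |

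Rows 1 and 2 are conflicts between sentence and table, and they run in opposite directions. Rows 3 to 5 are departures from the protocol that sentence and table share.

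Now take a subject who had a baseline scan but lacks one target measurement. The table's baseline clause is not triggered, so later PD or death is an event by default. If the sentence covers partly missing data, this subject is censored at randomization unless death comes early.

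**Size (illustration only).** Inputs: about 60 subjects per arm (Protocol 4.1.1); median PFS 17.2 months on durvalumab (Protocol 1.1), taken as exponential; scans at weeks 8 and 16 (Protocol Table 5). The documents do not give the share q of PFS events that are deaths without prior PD, so q is assumed to be 5% to 20%.

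Cumulative event probability: F(t) = 1 − exp(−t × ln 2 / 17.2).

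- F(week 8) = 7.1%; F(week 16) = 13.8%; F(12 months) = 38.3%, or about 23 of 60.

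Chance that a subject with no baseline assessment has a countable event by 12 months:

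- Protocol: 38.3%.
- Sentence, deaths before week 16 only: q × 13.8% = 0.7% to 2.8%.
- Table, PD at week 8 only: (1 − q) × 7.1% = 6.8% to 5.7%.

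Sentence and table therefore disagree for about 0.7 + 6.8 = 7.5% (q = 5%) to 2.8 + 5.7 = 8.5% (q = 20%) of such subjects. Against the protocol, the sentence loses about 93% to 98% of their 12-month events and the table about 82% to 85%.

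**Effect on PFS-12 in one arm.** Suppose k subjects have an event before month 12 and all k are censored at day 0, with no other censoring before then. With 60 − 23 = 37 event-free subjects, the estimate moves from 37/60 = 61.7% to 37/(60 − k):

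- k = 1: 37/59 = 62.7%
- k = 2: 37/58 = 63.8%
- k = 3: 37/57 = 64.9%

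The standard error is √(0.617 × 0.383 / 60) = 6.3 points. The documents do not give the number affected; k is an assumption.

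**The case against.** Four points deserve weight.

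1. **The table governs.** SAP 3.4.2.4 says that the censoring guidance is in the table. This weakens the risk of divergent programming but does not remove it. The sentence is written as a rule in its own right, and strict use of the table would censor early deaths that the sentence keeps.
2. **The protocol defers to the SAP.** It does, so the SAP may add censoring rules. That does not license two different ones, and a departure from the stated definition should be visible.
3. **Progression without a baseline scan may be uninterpretable.** A lesion cannot be called new, or a non-target lesion called worse, without a reference. This stands for PD in subjects with no baseline scan. It does not apply to death. It also does not apply when a baseline scan exists and only a measurement is missing, since new lesions or unequivocal non-target progression suffice for PD (Protocol Appendix F; SAP 7.1.3).
4. **Few subjects qualify.** Entry requires a measurable lesion (Protocol 4.1.2) and a screening scan (Protocol Table 5). This stands and limits the size.

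A reader might infer more than the documents support:

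- *That the sentence censors every subject with missing baseline data.* It does not: early deaths remain events.
- *That the sentence alone discards later events.* With no baseline assessment, the table discards them too.
- *That one unmeasured lesion certainly triggers the sentence.* SAP 3.4.2.1 uses similar wording for incomplete data at later visits, but SAP 7.1.1 and 7.1.3 use a more specific phrase for single missing measurements. The meaning is open.
- *That duration of response is affected through the shared censoring dates.* SAP 3.4.2.1 makes subjects with missing baseline lesion data non-evaluable for best response, and SAP 3.4.2.2 evaluates only confirmed responders, so they never enter that analysis.

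**Conclusion.** The inconsistency is real. Sentence and table give opposite outcomes in two situations, and their triggers differ. For subjects with no baseline assessment, both also censor later PD and deaths that Protocol 4.8.3 and the opening of SAP 3.4.2.4 count.

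The case for change rests on reproducibility and agreement with the protocol definition, not on size. A shift of 1 to 3 points in PFS-12 depends on 1 to 3 affected subjects with events in one arm, exponential PFS with a 17.2-month median, and no other early censoring. It lies well inside one standard error, on a secondary endpoint in a study whose sample size has no power basis (Protocol 4.8.2). The documents do not support a claim of material bias.

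**What to change.** State one rule, in the same words, in Table 3.4.1 and in the sentence below it:

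- Death stays a PFS event despite missing baseline data. So does PD that can be documented without the missing measurement: new lesions or unequivocal non-target progression, where a baseline scan allows the judgement. Both remain subject to the existing rule on two or more missed assessments.
- Censor at randomization only subjects with no baseline assessment and no such event. Say explicitly how PD recorded at the first scan is handled when there was no baseline scan, because sentence and table differ there now.
- Keep the separate clause for no post-dose assessment, with its early-death exception.
- Use one trigger term and say whether it includes partly missing data.

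Simply aligning the sentence with the present table row would not do: it would drop early deaths that the sentence now keeps and leave later deaths censored.

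If the sponsor prefers the wider censoring, the SAP should declare the departure from the protocol definition and add a sensitivity analysis using that definition. The cost is a revised sentence and table row and a check of the PFS code; the alternative adds one sensitivity output.
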